### 6.3 Subject Exclusion Criteria

1. History of hemolytic anemia or thalassemia
2. Current treatment or known prior treatment with ribavirin
3. Active infection or serious underlying medical condition that would impair the patient's ability to receive protocol treatment.
4. Current therapeutic anticoagulation with Coumadin (warfarin)
5. Known brain metastases

## 7.1 RECRUITMENT PLAN

Potential research subjects will be identified by a member of the patient's treatment team, the protocol investigator, or research team here at Memorial Sloan-Kettering Cancer Center (MSKCC). If the investigator is a member of the treatment team, s/he will screen their patient's medical records for suitable research study participants and discuss the study and their potential for enrolling in the research study.

The principal investigator may also screen the medical records of patients with whom they do not have a treatment relationship for the limited purpose of identifying patients who would be eligible to enroll in the study and to record appropriate contact information in order to approach these patients regarding the possibility of enrolling in the study.

During the initial conversation between the investigator/research staff and the patient, the patient may be asked to provide certain health information that is necessary to the recruitment and enrollment process. The investigator/research staff may also review portions of the medical records at MSKCC in order to further assess eligibility. They will use the information provided by the patient and/or medical record to confirm that the patient is eligible and to contact the patient regarding study enrollment. If the patient turns out to be ineligible for the research study, the research staff will destroy all information collected on the patient during the initial conversation and medical records review, except for any information that must be maintained for screening log purposes.

In most cases, the initial contact with the prospective subject will be conducted either by the treatment team, investigator or the research staff working in consultation with the treatment team. The recruitment process outlined presents no more than minimal risk to the privacy of the patients who are screened and minimal PHI will be maintained as part of a screening log. For these reasons, we seek a (partial) limited waiver of authorization for the purposes of 1) reviewing medical records to identify potential research subjects and obtain information relevant to the enrollment process; 2) conversing with patients regarding possible enrollment; 3) handling of PHI contained within those records and provided by the potential subjects; and 4) maintaining information in a screening log of patients approached.

## 8.1 PRETREATMENT EVALUATION

- Complete medical history including current medications, physical examination including evaluation of ECOG performance status within 14 days prior to therapy.
- Pathology review at MSKCC
- The following laboratory studies will be obtained within 14 days prior to therapy:  
Complete blood count with white blood cell differential and platelet counts;  
Comprehensive profile (including electrolytes, bicarbonate, blood urea nitrogen (BUN), creatinine, glucose, alkaline phosphatase, aspartate aminotransferase (AST), alanine aminotransferase (ALT), total bilirubin, total protein, albumin, and glucose); prothrombin time and activated partial thromboplastin time
- Serum pregnancy test for women of childbearing potential within 14 days prior to therapy.
- Electrocardiogram within 8 weeks prior to therapy
- Baseline cross-sectional imaging of the known sites of disease (CT or MR) within 4 weeks prior to therapy

## 9.0 TREATMENT/INTERVENTION PLAN

### 9.1 Clinical Plan

Study subjects will self-administer ribavirin 1400 mg PO BID (total dose, 2800 mg/day).

Ribavirin should be taken with food, not in a fasting condition.

All patients will complete pill diaries to document administration of study drug. Patients should be instructed to bring completed pill diaries and all pill bottles to each visit.

Cycle length is 28 days with continuous dosing. Clinic visits for safety assessments and routine laboratory studies will occur weekly in Cycle 1, in weeks 1 and 3 of Cycle 2, and on Week 1 of subsequent cycles ( $\pm$  3 days). Although clinic visits and lab tests should generally occur on the same day each week to facilitate continuity with providers, there is no requirement regarding the day of the week of these visits.

Toxicities will be graded according to NCI CTCAE version 4.

Cross sectional imaging (CT or MRI) is obtained at baseline and q2 cycles. Imaging scans will be scheduled to occur in the last week ( $\pm$  2 days) of each even-numbered cycle. However, after completion of cycle 4, the interval between scans may be increased to q3 cycles, at the discretion of the investigator.

Response assessments will follow RECIST 1.1 criteria (See Section 12).

Patients may remain on study until disease progression or unacceptable toxicity. There will be a post-treatment visit 30 days ( $\pm$  7 days) from last dose of drug for patients who maintain active follow up. If a patient is unable to attend the post-treatment visit due to medical or logistical issues or lost to follow-up, this will not be a protocol violation.

### 9.2 Immunohistochemistry (IHC)

Anti Gli-1 antibody (Glioma associated oncogene 1; H-300 rabbit polyclonal, Santa Cruz Biotechnology, sc-20687) has been used extensively for IHC in studies of cervix cancer and head and neck cancer [35, 36] and will be optimized for IHC in our Pathology Core. Formalin-fixed paraffin-embedded (FFPE) slides will be prepared in the Department of Pathology according to standard practices, and will be analyzed by [name]. Archived FFPE pre-treatment tumor samples will be processed for IHC detection of Gli-1 and scored by the study pathologist (scale 0-3 dichotomized to low/high).

For any patients who initially experience a radiographic response to ribavirin by RECIST 1.1 (confirmed or unconfirmed), at time of subsequent disease progression a research tumor biopsy will be obtained (unless such biopsy is deemed to pose unacceptable safety risk). Gli-1 expression will be assessed by IHC, in an effort to explore if increased Gli-1 expression (compared with pre-treatment tissue) may be associated with acquired resistance to ribavirin in patients with HPV-related malignancies. These post-treatment biopsies should generally be obtained within 2 weeks of the last dose of ribavirin, although it will not be considered a violation if the biopsy occurs outside of this time window. The gauge of the needle will be at the discretion of the interventional radiologist, although 18 gauge is preferred.

## MEMORIAL SLOAN-KETTERING CANCER CENTER

IRB#: 14-211 A (7)

APPROVED: 19 DEC 2016

Post-treatment biopsies will not be obtained in patients who do not initially respond to ribavirin.

(Note: Pharmacokinetics (PK) will not necessary for this study. PK for standard dosing of ribavirin was established in the 1980s, and PK for escalated ribavirin dosing in cancer was investigated in NCT00559091, NCT01056523, NCT01056757, and NCT01309490.)

## 10.0 EVALUATION DURING TREATMENT/INTERVENTION.

		Cycle 1	Cycle 2	Cycle ≥3	Post Treatment d
	Baseline	Weeks 1, 2, 3 and 4	Weeks 1 and 3	Week 1	
History and Physical	X	X	X	X	X
CBC, Comp panel	X	X	X	X	X
PT/aPTT	X				
Serum Pregnancy Test	X				
EKG a	X				
Radiologic Assessment (CT or MRI) b	X		X	X	
Archival Tissue	X				
Research biopsy c					X c
Adverse Event and Concomitant Medications Monitoring		Continuous Monitoring for Adverse Events			
Ribavirin		Continuous BID dosing			

a Baseline EKGs to be performed within 8 weeks prior to treatment

b Radiologic assessments occur at baseline (within 4 weeks of starting treatment) and q2 cycles. Imaging scans will be scheduled to occur in the last week ( $\pm$  2 days) of each even-numbered cycle. However, after completion of cycle 4, the interval between scans may be increased to q3 cycles, at the discretion of the investigator.

c Research biopsy at time of progression of disease is only for patients who experience initial radiographic response. When done, every effort should be made to obtain the research biopsy within 2 weeks of the last dose of ribavirin.

d The post treatment evaluation should occur 30 days ( $\pm$  1 week) after the last dose of ribavirin, for patients who maintain active follow up. The one exception is the post-treatment biopsy for patients who had previously responded (see footnote b)

## 11.1 TOXICITIES/SIDE EFFECTS

### 11.2 General Considerations

#### Ribavirin Toxicities:

Hematologic: anemia, thrombocytopenia, leukopenia, lymphopenia

Gastrointestinal: anorexia, nausea, diarrhea

Hepatic: elevated liver function tests

Pulmonary: dyspnea, cough

Reproductive: may be teratogen

Constitutional: fatigue, musculoskeletal pain

Dermatologic: alopecia, pruritus, rash

Neurologic: headache, dizziness

Endocrine and metabolic: hyperuricemia

The listed ribavirin toxicities include those side effects described in the treatment of hepatitis C in which ribavirin may be given in combination with peginterferon alfa [13-16], and those side effects described in other settings including oncology research in which ribavirin was given at doses up to 1400 mg po BID [37][17, 21].

Even when the patient meets criteria for continued treatment at full dose per the protocol, the investigator retains the discretion to delay the next treatment and/or reduce ribavirin dose if there are safety concerns and/or logistical issues. Any dose reductions not specified in the protocol should be discussed with the principal investigator.

Doses that have been reduced for toxicity must not be re-escalated.

Treatment delays of up to 21 total days per cycle are allowed in a given cycle. Any patient who requires a treatment delay of >21 days, for medical and/or logistical reasons, in a given cycle should be removed from study.

If an investigator feels that a patient requires a dose reduction and/or dose delay other than those specified herein, this may be allowed after communication with the Principal Investigator, and would not be considered protocol violation. If the Principal Investigator is unavailable, Co-PI or designated covering investigator may address such issues as they arise.

Dose modification guidelines in this section are only for those adverse events thought to be at least possibly related to ribavirin.

#### Dose Modification Scheme

Dose Level	AM/PM Dose	Total Daily Dose
Full Dose	1400 mg PO BID	2800 mg
Dose Level Minus 1	1000 mg PO BID	2000 mg
Dose Level Minus 2	800 mg PO BID	1600 mg
Dose Level Minus 3	600 mg PO BID	1200 mg

## 11.3 Hematologic Toxicity Management

### Hemoglobin

The most common toxicity requiring dose reduction for ribavirin is anemia.

For any patient who experiences a fall in hemoglobin of  $> 3$  g/dL (from Day 1 value; or from the hemoglobin value at the time of the previous dose reduction) and/or a drop in hemoglobin level to  $< 8.0$  g/dL, ribavirin dose will be decreased by one dose level.

Packed Red Blood Cell (PRBC) transfusion for symptomatic anemia is allowed, at the discretion of the investigator. However, any PRBC transfusion must be accompanied by dose reduction by one dose level. For any patient who requires PRBC transfusion, repeat complete cell count should be obtain within 1 week after completion of the transfusion to provide a new baseline hemoglobin level for consideration of subsequent hemoglobin levels.

### Absolute Neutrophil Count (ANC) and Platelets

ANC (K/mcL) and Platelet Count (K/mcL)
ANC $\geq 1.0$ and Plts $\geq 100$ : Treat without dose reduction.
ANC $< 1.0$ and/or Platelets $< 100$ : Hold. If repeat ANC the next week $\geq 1.0$ and repeat Plts next week $\geq 100$ , resume treatment. Dose reduction by one dose level is not mandatory, but is allowed at the discretion of the investigator.
Febrile Neutropenia *. Hold until resolution. When ANC $\geq 1.5$ and afebrile and Plts $\geq 100$ , may proceed but reduce by 1 dose level

Dose delays and dose reductions are not required for uncomplicated leukopenia, uncomplicated lymphopenia, or other abnormal values in the complete blood cell count (other than hemoglobin ANC, and platelets) without clinical consequence.

### 11.3 Hepatic Toxicity Management

#### 11.3.1 Alkaline Phosphatase, ALT, AST

If AST and ALT are both elevated, the more abnormal of the two values (AST or ALT) should be used in determining the dose.

AST or ALT:				
ALK PHOS: ≤ 1.5 X ULN	≤ ULN	>1X but ≤1.5X ULN	>1.5X but ≤5X ULN	>5X ULN
	Full Dose	Full Dose	Treat at Full Dose, Or Treat at Reduced Dose, Or Hold, at discretion of investigator*	Hold*, 
	Full Dose	Full Dose	Hold or Treat at Reduced Dose, at discretion of investigator*	Hold*, 
	Full Dose	Hold*	Hold*, 	Hold*, 
>1.5 X but ≤ 2.5X ULN	Full Dose	Full Dose	Hold*, 	Hold*, 
>2.5X but ≤ 5X	Full Dose	Hold*	Hold*, 	Hold*, 
>5X ULN	Hold*	Hold*	Hold*, 	Hold*, 

\*If treatment is held, treatment should not resume until liver function tests have “recovered”, maximum 21 days. “Recovered” is defined as meeting requirements for treatment according to this table.

 Upon recovery, resume treatment at full dose or reduce by 1 dose level, at the discretion of the investigator.

 Upon recovery, resume treatment at next lower dose level

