## 11.4 Renal Toxicity

If serum creatinine is  $\geq 1.5$  on planned treatment date, estimate the creatinine clearance (CrCl) by the Cockcroft and Gault Equation.

Calculated Creatinine Clearance (CrCl)	Management
$\geq 45$ ml/min	Hydrate as clinically indicated. May treat at full dose, treat at next lower dose level of ribavirin, or hold treatment, at the discretion of the investigator.
$< 45$ ml/min	Hold treatment for the week and hydrate as clinically indicated.  If repeat CrCl $\geq 45$ ml/min, may resume treatment at the next lower dose level of ribavirin

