## 11.5 Diarrhea

### Grade 1 or Grade 2 Diarrhea:

Ribavirin treatment may be continued at full dose, continued at the next lower dose level, or held. Antidiarrheals may be used as needed. Dose reduction is at the discretion of the investigator.

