### Grade 3 Diarrhea:

In the event of diarrhea requiring hospitalization (ie, Grade 3), supportive measures may include hydration, octreotide, and antidiarrheals.

Ribavirin treatment will be held until diarrhea has improved to  $\leq$  Grade 1, with dose reductions as follows:

If Grade 3 diarrhea duration is  $\leq 48$  hours, the next treatment may be given at full dose or at the next lower dose level, at the discretion of the investigator.

If Grade 3 diarrhea duration is  $> 48$  hours, subsequent ribavirin should be given at the next lower dose level

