### 11.7 Non-hematologic toxicity not otherwise specified

Dose delay and/or dose reduction is optional at the discretion of the investigator as regards the following  $\geq$  grade 3 adverse events: dental adverse events, hearing-related adverse events, INR or aPTT elevation, insomnia, weight gain or weight loss, SIADH, low bicarbonate, low albumin, hypophosphatemia. Similarly, the decision regarding whether to institute dose modifications for grade 2 or 3 fatigue will be at the discretion of the investigator.

For non-hematologic toxicity not otherwise specified:

$\geq$  Grade 3: Interrupt until resolved to  $\leq$  grade 1, then:  
If resolution to grade  $\leq 1$  in  $\leq 7$  days, resume ribavirin at the current dose level or at next lower dose level, at investigator discretion  
If resolution to grade  $\leq 1$  in  $> 7$  days, resume ribavirin at one lower dose level

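### Section 11 defines Full Dose as 1400 mg BID and bars re-escalation, yet some hepatic and diarrhea rules do not list staying at an already reduced dose

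*Combined protocol and SAP*

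**What the plan says.** The Dose Modification Scheme lists four levels: Full Dose (1400 mg BID), Minus 1 (1000 mg BID), Minus 2 (800 mg BID) and Minus 3 (600 mg BID). Section 11.2, General Considerations, adds a rule with no stated exception: "Doses that have been reduced for toxicity must not be re-escalated".

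Patients can reach a reduced level by a mandatory route. Under the Hemoglobin rule, a fall of more than 3 g/dL or a value below 8.0 g/dL means that "ribavirin dose will be decreased by one dose level", and any red cell transfusion must also be accompanied by a one-level reduction. The same rule states: "The most common toxicity requiring dose reduction for ribavirin is anemia".

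The later toxicity rules use the term full dose as follows:

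- **Section 11.3.1 (AST, ALT, alkaline phosphatase), table:** several cells say Full Dose and nothing else.
- **Section 11.3.1, footnote 1:** "Upon recovery, resume treatment at full dose or reduce by 1 dose level, at the discretion of the investigator".
- **Section 11.5, Grade 3 diarrhea lasting 48 hours or less:** "the next treatment may be given at full dose or at the next lower dose level".
- **Section 11.3.2 (bilirubin above ULN and up to 1.5 times ULN):** hold, full dose or reduced dose, at discretion.
- **Section 11.4 (creatinine clearance of at least 45 ml/min):** "May treat at full dose, treat at next lower dose level of ribavirin, or hold treatment, at the discretion of the investigator".
- **Section 11.5, Grade 1 or 2 diarrhea:** "Ribavirin treatment may be continued at full dose, continued at the next lower dose level, or held".

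Section 11.7 uses another term when other non-hematologic toxicity resolves within 7 days: "resume ribavirin at the current dose level or at next lower dose level". Section 13.0 removes from study any patient who needs a reduction below Minus 3.

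**The concern.** Full Dose is the name of one row of the scheme, and none of the rules that use the term is limited to patients who have never been reduced. If a patient is already at Minus 1, Minus 2 or Minus 3, for example after anemia, treating at full dose in the defined sense is a re-escalation, which Section 11.2 forbids. Where a rule offers only full dose or one level lower, the patient's present dose is not among the listed choices.

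Section 11 does have a phrase for staying put, and uses it in Section 11.7. A reader therefore cannot assume that full dose means the current dose elsewhere. No sentence says so, and none says which rule takes precedence.

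Two clinicians, or one clinician at two visits, could read the same text and treat the same reduced patient differently after a second toxicity. From Minus 3, the reading could bear on whether the patient stays on study.

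**Working it through.** **1. Dose levels.** Inputs are the BID doses in the Dose Modification Scheme. Daily dose = 2 × BID dose, which reproduces the plan's totals: 2 × 1400 = 2800, 2 × 1000 = 2000, 2 × 800 = 1600, 2 × 600 = 1200 mg.

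**2. What the two listed options mean for a reduced patient.** Ratio = 2800 ÷ current daily dose.

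| Current level | Daily dose (mg) | Full Dose as defined | One level lower |
|---|---|---|---|
| Minus 1 | 2000 | 2800/2000 = 1.40 times (+800 mg, +40%) | 1600 mg/day |
| Minus 2 | 1600 | 2800/1600 = 1.75 times (+1200 mg, +75%) | 1200 mg/day |
| Minus 3 | 1200 | 2800/1200 = 2.33 times (+1600 mg, +133%) | Removal (Section 13.0) |

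Section 11.2 bars every increase in the third column.

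**3. Rules side by side, with Full Dose read as defined.**

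| Rule | Listed options | Position for a reduced patient |
|---|---|---|
| 11.3.1, cells with Full Dose alone | Full Dose | Conflicts with the ban; no alternative in the cell |
| 11.3.1, footnote 1 | Full dose, or one level down | Barred increase or further reduction |
| 11.5, Grade 3, 48 hours or less | Full dose, or one level down | Barred increase or further reduction |
| 11.3.2, above ULN to 1.5 times ULN | Hold, full or reduced | Discretionary; the ban can simply remove one option |
| 11.4, clearance of at least 45 ml/min | Full, one level down or hold | Discretionary; as above |
| 11.5, Grade 1 or 2 | Continue at full, continue one level down, or hold | Weakest: a patient at a lower dose cannot continue at 1400 mg BID |
| 11.7, resolved within 7 days | Current level, or one level down | No conflict |

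The conflict does not arise in the branches that require the next lower level after a hold (AST or ALT above 5 times ULN, bilirubin above 1.5 times ULN, clearance below 45 ml/min, Grade 3 diarrhea beyond 48 hours), or in Grade 4 diarrhea, where the patient goes off study if it is felt to be treatment related.

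The row labels of the hepatic table are damaged in the available text. The point rests only on there being cells that say Full Dose alone, not on which alkaline phosphatase band each belongs to.

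**4. Design figure.** Section 14.0 gives 0.09 as the chance of 0 or 1 responses in 12 at a true rate of 30%. Exact binomial: 0.7^12 + 12 × 0.3 × 0.7^11 = 0.0138 + 0.0712 = 0.0850, which rounds to 0.09. No dose rule enters this calculation, so neither the sample size nor the rule of at least 2 responses in 12 changes.

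**The case against.** The strongest reply is that this is loose terminology, and that clinicians can comply with everything as written. Much of that stands.

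- **Discretion.** Section 11.2 lets the investigator reduce ribavirin even when a patient qualifies for full-dose treatment. It also says that unlisted reductions, after communication with the principal investigator, are not violations. A reader might infer that keeping a patient at the reduced dose breaches the toxicity table. It does not.
- **Permission against prohibition.** Apart from the hepatic cells with a single instruction, full dose is an option. A firm ban can limit an option, and both are obeyed by choosing the lower level or, where offered, a hold. A reader might infer that every rule using the term contradicts Section 11.2; the bilirubin, renal and Grade 1 or 2 diarrhea rules do not support that.
- **The literal reading proves too much.** It would send an anemia-reduced patient with normal liver tests back to 1400 mg BID, which would defeat the Hemoglobin rule. The table may have meant no change on hepatic grounds, but the text does not say so.
- **Inferences the documents do not support.** The statement about anemia ranks reasons for reduction; it does not show that reduced patients are the most likely to have a second toxicity. Nor is distortion of the Section 14.0 tabulation of dose reductions shown, since a re-escalation is not itself a reduction. Differences between sites cannot arise in a single-center trial.

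None of this defines full dose or adds the current level to footnote 1 or the short-duration Grade 3 diarrhea rule. A clinician reaches that choice only through the general discretion clause.

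**Conclusion.** The point holds in limited form. It is firm in three places: the hepatic cells that say Full Dose alone, footnote 1 of that table, and the rule for Grade 3 diarrhea of 48 hours or less. Read as defined, the cells give a reduced patient only a barred increase. The other two rules give that increase or a further reduction, which from Minus 3 means leaving the study.

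The step sizes are upper bounds on the effect of a literal reading, and apply only if a clinician follows the toxicity rule over the ban. The documents give no basis for estimating how often a reduced patient would meet one of these rules, so no frequency is claimed. The conclusion assumes that Full Dose carries the meaning in the scheme, which is the only definition in the protocol. It is a wording conflict that bears on safety and on consistent dosing between clinicians or visits, and it should be corrected.

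**What to change.** Reconcile Sections 11.3.1, 11.3.2, 11.4 and 11.5 with Section 11.2, the Dose Modification Scheme, Section 11.7 and Section 13.0. In each toxicity rule, state:

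1. whether full dose means the 1400 mg BID level or the level the patient was taking at onset; and
2. whether the re-escalation ban governs that rule or is excepted from it.

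For footnote 1 and the short-duration Grade 3 diarrhea rule, also state whether staying at the current level is an option, and what applies to a patient at Minus 3. The sponsor's clinical team should decide the content; this review takes no view on which rule is right.

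The cost is a wording amendment to Section 11, with no added visits, patients or analyses.
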